6.6 Ventricular Arrhythmia Induction Protocol

A standardized induction protocol is performed using programmed ventricular stimulation from the RV apex. The protocol is based on a prior study evaluating a range of induction protocols used to test inducibility before and after AAD administration in the EP lab.³⁹ Sedation and vasopressor infusion is maintained at constant levels throughout the study protocol and, any changes warranted for clinical care will be documented. The pacing cycle length is 8 beats followed by extrastimuli (ES) and a 3 second rest period. The basic cycle length of the pacing drive train (S1 – S1) is 600 ms (100 bpm). The first extrastimulus (S2) is introduced at 300 ms and decremented by 10 ms to VERP or 200 ms. S2 is then set to a coupling interval (S1 – S2) of VERP (or 200 ms) + 20 ms and a second extrastimulus (S3) added at a coupling interval of S1-S2 + 50 ms and scanned to refractoriness or a minimum coupling interval of 200 ms. The second extrastimulus is then set to its VERP + 20 ms and a third extrastimulus (S4) added at an initial coupling interval (S3 – S4) of S2 – S3 + 50 ms and scanned in to refractoriness or 200 ms. Thus up to 3 extrastimuli are added and the minimum coupling interval will not be shorter than 200 ms. The induction protocol is stopped when: 1) the primary endpoint is met, or 2) the induction protocol has been completed. The primary endpoint is an episode of sustained VT that lasts \geq 10 seconds or two episodes of non-sustained ventricular arrhythmia defined as VT or VF that lasts 3-9 seconds.

6.7 Pulmonary Artery (Swan-Ganz) Catheter Placement

The participant is supine and under deep sedation or general anesthesia during the procedure. Due to the creation of a complex electroanatomic map, it is critical that patients do not move during an ablation procedure. This is also ideal for comparative hemodynamic assessments. The transducer is placed midway between the level of the anterior and posterior surfaces of the patient's chest and zeroed to atmospheric pressure. The balloon-tipped PA catheter is placed via a femoral venous sheath and advanced to the right atrium (RA). A combination of pressure wave form interpretation and fluoroscopy is used to guide the PA catheter through the RV to the distal PA. The PA catheter remains in the same position during the pre and post-drug hemodynamic measurements.

6.8 Pressure Measurement

Recordings are obtained to measure the following pressures: mean RA, PA systolic, PA diastolic, and mean PA. All pressures are recorded as the average of 3 measurements obtained at end expiration.

6.9 Arterial Blood Pressure Measurement

As part of an ablation procedure, invasive arterial blood pressure is monitored via an arterial pressure catheter (femoral and/or radial artery). As clinical endpoints, systolic, diastolic, mean and pulse pressures are recorded immediately prior to study drug administration, and then every 2 minutes after drug administration during the research protocol (except during pacing maneuvers). Changes in vasopressor infusion rate and boluses are also recorded.

6.10 Cardiac Output, RV Function, and Vascular Resistance Assessment

Cardiac output is measured using the Fick method. A pre-study drug cardiac output is recorded, and then cardiac output is sampled 4 times post-study drug for the purposes of Aim 2 and for PK/PD analysis. Indices of RV function are calculated including RV stroke volume index and PA pulsatility index. Systemic and pulmonary vascular resistance are also calculated. Note, if the pre-study drug mixed venous oxygen saturation (SvO₂) is <50%, the research protocol will be stopped, and the study drug will not be administered.

6.11 ECG Intervals

ECG intervals (RR, PR, QRS, QT) are recorded from a continuous 12-lead tracing obtained prior to study drug administration and then for 20 minutes after study drug. Measurements are made offline at a sweep speed of 100 mm/s. Measurements are made every minute during the post-study drug period. Measurements are recorded as the median of 3 beats.

6.12 Pharmacokinetic (PK)-Pharmacodynamic (PD) Analysis

PK/PD analysis will be performed by [name] (Lipscomb University). Ryanodex is a new formulation of dantrolene (nanoparticle suspension for injection) with enhanced aqueous solubility designed for rapid I.V. administration. The FDA determined that our proposal is exempted from requirements for an Investigational New Drug application (see accompanying letter from FDA). The PK of Ryanodex have been investigated in healthy volunteers at a dose range of 1 to 2.5 mg/kg and demonstrated a dose-proportional increase in dantrolene exposure with a peak concentration observed 1 minute after drug administration. Mean PK parameter estimates are independent of dose with a mean half-life of 10 hours, volume of distribution of 36.4 L, and systemic clearance of 2.5 L/hr. One major determinant of the short-term effects of many cardiac drugs is the concentration of drug within the myocardial tissue. Previous *in-vivo* studies evaluating the myocardial uptake of drugs in humans using a transcoronary blood sampling technique have demonstrated that lipophilic drugs like dantrolene exhibit rapid uptake into myocardial tissue with peak myocardial tissue content (1-4% of dose administered) being achieved within 0.5-5 minutes after I.V. bolus.^{56,57} To define the PK/PD relationship of dantrolene and its short-term effect on the specific hemodynamic (PA wedge pressure, Fick cardiac output) and EP parameters (electrocardiogram intervals [RR, PR, QRS, QT]), femoral venous, arterial, and PA distal blood samples will be collected simultaneously from indwelling sheaths in all subjects at the pre-dantrolene timepoint and at 5, 10, 15, and 20 minutes post-dantrolene. Arterial drug concentrations will be assumed to represent dantrolene concentrations present in the ascending aorta and reflect concentrations entering the coronary circulation. As such, the temporal relationship between dantrolene concentrations (arterial and venous) and peak hemodynamic and EP effects will be evaluated using PK/PD modeling approaches to determine direct response correlations or a potential time lag in response.

Following the PK/PD phase of the study, PK sampling will be performed by collecting up to seven blood samples per subject that are drawn at variable time intervals. Blood samples will be 2 mL each and no more than a total of 15 mL of blood will be drawn post-operatively. PK will be analyzed using both an intensive and sparse (population) PK approach.⁵⁸ Dantrolene plasma concentrations in all blood samples will be determined using liquid chromatography coupled with tandem mass spectrometry (LCMS-MS) with an assay threshold of 5 ng/ml. Plasma concentration-time data from individual subjects will be imported into Phoenix WinNonlin® 8.0 software (Certara USA, Inc., Princeton, NJ) to estimate the PK parameters of dantrolene from population PK approaches.

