6.2 List of Encounters Detailing the Clinical and Research Activities

Encounter 1: Enrollment and Informed Consent

- Performed by the study team in the Vanderbilt Arrhythmia Clinic or Vanderbilt University Hospital.

Encounter 2: Time of Ablation

- The participant will arrive the morning of ablation to the EP pre-op holding room and undergo standard preparations for ablation according to the clinical protocols (e.g. labs, vitals, exam, procedural consent).
- The participant will undergo baseline muscle (grip) and respiratory (NIF) strength testing in the pre-op area.
- The participant is then transported to the operating room (EP lab) where standard of care ablation is performed under the direction of the clinical team. See section 6.1 for full details.
- Research activities will begin after completion of the ablation portion of the ablation procedure. Research activities occur concurrently with clinical activities and are performed by a dedicated physician and nurse team to avoid extending overall case time.
- The clinical post-ablation EP study with programmed ventricular stimulation will serve as the baseline (pre-dantrolene) assessment of cardiac electrophysiology parameters (conduction and refractoriness) and ventricular arrhythmia inducibility. Data analyses are performed offline following the case to avoid adding procedural time. See sections 6.3 to 6.6 for full details.
- Hemodynamic monitoring is routinely performed during ablation with an arterial line and pulmonary artery (PA) catheter (aka. Swann-Ganz Catheter). See sections 6.7 to 6.10 for full details. The pre-dantrolene arterial blood pressure mean right atrial, PA systolic, PA diastolic, mean PA pressure, and pulmonary artery wedge pressures will be recorded.
- Blood samples will also be drawn for calculation of a Fick cardiac output and for the pharmacokinetic (PK)/pharmacodynamic (PD) analysis. See section 6.12 for full details of the PK/PD analysis. A 2 mL sample from the femoral venous, arterial, and distal PA catheter will be collected.
- I.V. dantrolene will be administered over 3 minutes. Peak drug levels occur rapidly allowing the data collection protocol to proceed without delay.
- The post-dantrolene hemodynamics will be recorded.
- The post-dantrolene EP study with programmed ventricular stimulation will be repeated.

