- A 2 mL sample from the femoral venous, arterial, and distal PA catheter will be collected at 5, 10, 15, and 20 minutes post-dantrolene. The total amount of blood collected during the ablation is 30 mL.
- Respiratory mechanics (tidal volume, rate, minute ventilation) and an arterial blood gas (ABG) will be measured at 0, 10, and 20 minutes, and need for additional respiratory support will be assessed continuously as is standard care (see Section 6.13).
- The clinical and research activities will be complete, and the participant will leave the operating room awake, extubated, and hemodynamically stable.
- The participant will undergo baseline muscle (grip) and respiratory (NIF) strength testing in the post-op recovery area and an ABG will be measured 120 minutes after study drug was initiated

Encounter 3: Post-ablation Day 0-2.

- Following ablation, the participant will be returned to the EP holding room. It is clinical standard-of-care for patients to remain in the hospital at least overnight for monitoring. They will be under nursing observation and on continuous cardiac telemetry and oximetry. They will be on strict bedrest until post-operative Day #1 and they will be ambulated with assistance the morning after the procedure.
- 2 mL blood samples will be drawn at intervals of 4 to 12 hours for up to 48-hours during the post-ablation period. No more than 15 mL total will be drawn. We will use indwelling catheters whenever possible for blood collections. All patients will have indwelling catheters throughout the duration of study, and we do not anticipate needing to perform phlebotomy with a fresh stick during the study. See section 6.12 for full details.

- The research protocol is complete when the participant is discharged from the hospital.

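### No drug concentration is taken before 5 minutes and time zero is undefined, so the early part of the PK/PD time-lag analysis rests on extrapolation

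*Combined protocol and SAP*

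**What the plan says.** Section 6.12 gives two early time marks. Plasma shows a "peak concentration observed 1 minute after drug administration" in healthy volunteers, and for lipophilic drugs as a class it cites "peak myocardial tissue content (1-4% of dose administered) being achieved within 0.5-5 minutes after I.V. bolus". It then plans PK/PD modelling of concentration against peak hemodynamic and EP effects, "to determine direct response correlations or a potential time lag in response".

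Blood is drawn "at the pre-dantrolene timepoint and at 5, 10, 15, and 20 minutes post-dantrolene". Section 6.2 repeats those times for all three sites and states that "I.V. dantrolene will be administered over 3 minutes". Neither section ties the minute marks to the start or the end of that push.

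On the response side, section 6.11 has ECG intervals read every minute for 20 minutes. Section 6.10 has cardiac output sampled four times after study drug, which matches the four draws. Section 6.12 adds up to seven later samples per subject and a population PK fit. No section names an observed peak concentration or time of peak as an endpoint.

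**The concern.** The schedule starts at or after the end of the interval in which, by the protocol's own account, plasma and heart-tissue levels peak. To tell a direct effect from a short lag, the data need a period in which plasma and effect site differ. Without an early concentration, that period is filled in by the model. The ECG readings at 1 to 4 minutes are paired with predicted levels only, and cardiac output has neither a level nor a reading there.

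The undefined clock adds to this. If time runs from the end of the push, the 5-minute draw is 4 minutes after the stated peak. If it runs from the start, that draw is 2 minutes after the push ends and about 1 minute after the peak. A lag of a few minutes cannot be interpreted unless time zero is fixed, and early samples not taken cannot be recovered later.

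**Working it through.** **Inputs.** From section 6.12: clearance 2.5 L/h, volume 36.4 L, half-life 10 h, draws at 0, 5, 10, 15 and 20 min. From section 6.2: 3-min push, three sites, 2 mL each, 30 mL in total. From section 10: 56 dantrolene patients. The documents reviewed give no distribution-phase figures and no lag, so these are assumed and varied.

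**1. The plan's own figures reproduce.** Half-life = ln 2 × 36.4 / 2.5 = 10.09 h (stated 10). Blood = 5 times × 3 sites × 2 mL = 30 mL (stated 30).

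**2. One compartment.** k = 2.5 / 36.4 = 0.0687 per hour.
- From 5 to 20 min: exp(−0.0687 × 15/60) = 0.983, a fall of 1.7%.
- From peak to 5 min: exp(−0.0687 × 4/60) = 99.5% remaining (end-of-push clock), or exp(−0.0687 × 1/60) = 99.9% (start-of-push clock).

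On this model the 5-min value is almost the peak.

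**3. With a fast distribution phase.** Let a fraction f of the 1-min level decay with half-life h: r(t) = f·exp(−ln 2 · t/h) + (1 − f)·exp(−kt). For f = 0.5 and h = 2 min, r(4) = 0.5 × 0.25 + 0.5 × 0.995 = 0.62. Over f = 0.2-0.8 and h = 1-10 min, the 5-min level is 25-95% of the peak (end clock) or 60-99% (start clock). The unsampled part may be negligible or large, and the planned samples do not observe it directly.

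**4. Precision of the lag constant as planned.** Effect compartment: dCe/dt = ke0(C − Ce), effect proportional to Ce. Assumed: two compartments with V1 of 9 or 18 L and V2 = 36.4 − V1, distribution half-life 3 min, 15% concentration error, response error 30% of the maximum effect, 56 patients, seven later samples, no between-patient variability (so the figures are optimistic). Relative standard error of ke0 from the Fisher information, with the range over the two V1 values:

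| Lag half-life | ECG, start clock | ECG, end clock | Cardiac output, start clock | Cardiac output, end clock |
|---|---|---|---|---|
| 1 min | 9-12% | 15-23% | 24-26% | 114-204% |
| 2 min | 7-9% | 13-24% | 11-13% | 29-36% |
| 5 min | 6-8% | 11-16% | 10-12% | 14-19% |
| 10 min | 9-12% | 12-18% | 14-20% | 16-24% |

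The weak cells are cardiac output at lags under about 2 min, mainly on the end-of-push clock.

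**5. One arterial draw 1 min after the push, all four cardiac-output readings kept.** With V1 of 9-18 L, distribution half-life 1.5-4 min, effect half-life 1-5 min and either clock, the relative standard error of the ECG lag constant falls in every case. The reduction is about 1.1- to 7-fold, and more where the planned design is nearly unidentified (fast distribution, end-of-push clock). Blood = 30 + 2 = 32 mL.

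**6. Moving the 15-min set to 1 min after the push instead.** In a one-compartment effect model with concentration taken as known, the standard error of log ke0 for cardiac output falls 5.5-, 2.4- and 1.7-fold at half-lives of 1, 1.5 and 2 min (end clock). The gain is only 1.4-, 1.3- and 1.2-fold on the start clock, and on the end clock 1.27-, 1.13- and 1.08-fold at 3, 5 and 10 min. At 1 min after the push the effect is about 79%, 56% and 29% of plateau for half-lives of 1, 2 and 5 min. The four-reading mean therefore drops by about (1 − 0.79)/4 = 5%, (1 − 0.56)/4 = 11%, and 19% (the last computed directly, because later readings are also below plateau).

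**The case against.** A reader might infer that the peak and the lag analysis largely cannot be derived, or that a finding of no lag would simply reflect the schedule. The documents do not support that. The lag is to be estimated by modelling with a known dose and push duration, not read off an observed time of peak. ECG intervals, the EP part of the response data, are read every minute. Cardiac-output lags of about 3 minutes or more are estimable as planned. The protocol's own one-compartment figures make the 5-minute level nearly equal to the peak, so one cannot argue both that levels are flat and that the peak is lost without assuming a distribution phase. All of this stands.

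Three further points also carry weight. Heart-tissue content is never measured, and its cited window includes 5 minutes, so an earlier blood draw would not observe it. Elsewhere the plan counts from the start of drug (the 2-hour blood gas in section 6.2, the time covariates in section 10), which lends some support to the milder reading of the clock. And the pilot-study text that follows the section 3.3 heading was not in the copy reviewed, so any pilot support for the schedule could not be checked.

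What remains is that early concentrations are extrapolated without a check, short hemodynamic lags are weakly identified, and time zero is undefined.

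**Conclusion.** The concern holds in limited form. No concentration is measured before 5 minutes, so the peak and early distribution are extrapolated and the earliest ECG readings lack a measured concentration. Cardiac-output lags with a half-life under about 2 minutes are weakly identified: at 1 minute the relative standard error is 24-26% or 114-204%, depending only on which end of the push starts the clock. At 5-10 minutes it is 10-24%, and for ECG it is 6-24% throughout.

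These sizes rest on assumed compartment volumes, distribution and lag half-lives and error sizes, and on ignoring between-patient variability. The ECG range assumes a 3-minute distribution half-life; faster distribution can make it worse, and in one setting examined the ECG lag is nearly unidentified.

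The effect is confined to the exploratory PK/PD aim (Aim 2 in section 2.0). It does not touch the power of the EP, inducibility or hemodynamic primary endpoints, although section 10 also labels the hemodynamic endpoints Aim 2.

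**What to change.** In sections 6.2 and 6.12:
- Define time zero for the PK/PD draws as the end of the push, and record actual draw times. Record the start of the push as well, since the section 10 time covariates count from there.
- Add one 2 mL arterial concentration sample 1 minute after the push ends, to pair with the ECG readings.
- Keep the four three-site sets and their cardiac-output readings at 5, 10, 15 and 20 minutes.
- State that cardiac-output lags under about 2 minutes remain weakly identified, because the added draw carries no cardiac-output reading and an end-of-push clock is the less favorable case for them.

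Moving the 15-minute set to 1 minute would hold blood at 30 mL but is not advised. Section 6.10 uses those readings for Aim 2 as well as for PK/PD, and section 10 makes cardiac index a primary endpoint, so an early reading could dilute its post-drug mean by roughly 5-19%.

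The cost is an increase in intra-procedural blood from 30 to 32 mL, with the total in section 6.2 updated, and one timed draw from the indwelling arterial line that must be prepared before the push ends. The primary cardiac-index analysis is unchanged.

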6.13 Measurement of Respiratory Mechanics and Ventilation

To enhance the safety of the study protocol and enable research on the effect of dantrolene on respiratory mechanics, the study team will include cardiac anesthesiologists (Drs. [name], [name], [name], [name], and [name]) and will specifically study the effect of dantrolene on respiratory mechanics. Prior to the procedure, a baseline measurement of respiratory muscle strength will be obtained with a negative inspiratory force test (NIF), which is a quick, non-invasive bedside breathing test. During the procedure, to monitor adequacy of ventilation, maintain safety, and measure the effect of dantrolene administration on ventilation, the anesthesiologist will monitor respiration oxygenation as is standard care for all patients during procedures and surgeries. If the patient is already under general anesthesia with controlled ventilation (either with laryngeal mask airway [LMA] or endotracheal tube [ETT]), attempts will be made to have the patient spontaneously breathing with neuromuscular blockers reversed. These measurements include respiratory rate, minute ventilation, tidal volume, as well as arterial blood gas measurements (pH/pO₂/pCO₂/BE/Na/K/Cl/Ca). These measurements will be recorded prior to study drug administration and at 10 and 20 minutes after study drug administration. Finally, two hours and again at 24 hours after study drug administration, a NIF will be repeated to assess whether the respiratory muscle strength has returned to baseline. An arterial blood gas will also be repeated at 2 hours after study drug administration (sample obtained from the radial arterial line).

6.14 Measurement of Muscle Strength

To monitor the effect of dantrolene on muscle strength, a baseline assessment of handgrip strength will be obtained prior to the procedure using a dynamometer. Finally, two hours and again at 24 hours after study drug administration, an assessment of grip strength using the dynamometer will be repeated to assess whether the respiratory muscle strength has returned to baseline.

7.0 RISKS

Patients with structural heart disease and PVCs or VT who are undergoing ablation are at risk for complications by nature of their underlying disease process and the procedure. These risks are inherent to the patient population studied here. The risks of obtaining blood samples from phlebotomy of peripheral veins and existing venous lines are minimal. There are risks associated with inducing ventricular arrhythmias, however the pacing maneuvers used in this protocol are commonplace during ablation and have a long history of being used both clinically and for research purposes.^{59,60} There are risks associated with dantrolene (Ryanodex). A comprehensive list of adverse reactions from the Ryanodex brochure include skeletal muscle weakness, dyspnea, respiratory muscle weakness, dysphagia, somnolence, lightheadedness, tissue necrosis (only if extravasated into surrounding tissue), nausea, thrombophlebitis, urticaria, and anaphylaxis. Drug interactions include calcium channel blockers, therefore patients using calcium channel blockers are excluded from the trial. Precautions also include muscle relaxants, antipsychotic and antianxiety agents as they may potentiate weakness, somnolence, and dizziness with Ryanodex. The risk of adverse reactions are dose-dependent and we propose here to use the lowest approved dose of Ryanodex (1 mg/kg). Furthermore, a one-time dose of I.V. Ryanodex will be given in the EP lab while under the care of both the Cardiac EP and Anesthesiology teams. Collaborating investigators on this study include cardiac anesthesiologists who will be monitoring respiratory status and measuring respiratory mechanics, ventilation, and muscle strength which will add additional safety precautions to the protocol. According to standard clinical protocol following ablation, patients are on strict bedrest until post-operative Day #1 with continuous cardiac and respiratory telemetry. Participants will be ambulated with assistance for the first time on post-operative Day #1. This minimizes the risks associated with the potential for skeletal and respiratory muscle weakness and lightheadedness. Furthermore, the eligibility criteria for this trial will exclude participants with a history of skeletal muscle disorders (e.g. muscular dystrophy), pulmonary disease requiring supplemental oxygen or prior intubation, morbid obesity, or a history of dysphagia. According to the Ryanodex brochure, patients must not drive 48 hours after Ryanodex administration. However, the vast majority of patients undergoing ablation are on pre-existing driving restrictions because they have experienced recent ICD shocks and/or ventricular arrhythmias.

Table 3. Anticipated risks associated with dantrolene, PVC or VT ablation procedures, and the study protocol

Risks from Study Drug (Ryanodex)	Risks from ablation procedure
Flushing	Acute myocardial infarction
Somnolence	Anemia
Dysphonia	Arterial dissection
Dysphagia	Atrial fibrillation/flutter/tachycardia
Nausea	Back pain
Feeling abnormal	Bleeding
Headache	Cardiac or valvular injury
Vomiting	Cardiac insufficiency
Vision blurred	Cardiac perforation
Pain in extremity	Cardiogenic shock
Muscular weakness/asthenia	Cerebrovascular accident
Bradycardia (AV block, sinus node dysfunction)	Transient ischemic attack
Tachycardia	Cardiac ischemia
Infusion site pain/necrosis if extravasated	Chest pain
Dizziness/lightheadedness	Congestive heart failure
Dyspnea, respiratory muscle weakness	Death
Urticaria, skin erythema	Electromechanical dissociation
Thrombophlebitis	Epistaxis secondary to anticoagulation
Anaphylaxis	Headache

8.0 REPORTING OF ADVERSE EVENTS AND UNANTICIPATED PROBLEMS INVOLVING RISK TO PARTICIPANTS AND OTHERS

